--	--

[figure not shown]
	

• For patients in the sotagliflozin groups, missing data will be imputed as if the patients were on placebo throughout the study, where all patients' measurements including the on-treatment measurements will be considered as if the measurements were from the placebo group in the imputation model.

 
Each of the complete datasets will be analyzed by the Analysis of Covariance (ANCOVA) model with treatment groups (sotagliflozin 400 mg, sotagliflozin 200 mg, placebo), randomization stratum of HbA1c (<math>\leq 8.5\%</math>, <math>> 8.5\%</math>) at Screening, randomization stratum sex (male, female) and country as fixed effects, and Baseline HbA1c value as a covariate.
 
Results from each complete dataset will be combined to provide the adjusted least squares (LS) mean change in HbA1c from Baseline to Week 26 for each treatment group, as well as the between-group difference (comparing sotagliflozin 400 mg versus placebo) and the 95% confidence intervals (CIs) for the difference.
 
Summary statistics (for Screening value, Baseline value, observed values, and observed changes from Baseline) at scheduled visits will be provided for each treatment group. The summary will include the number of observations, mean, SD, standard error (SE), minimum, median, and maximum. Graphical presentations will also be used to examine trends over time using mean values (<math>\pm</math>SE) and mean changes from Baseline (<math>\pm</math>SE) at each of the scheduled visits (using observed cases [OC]).
 
Analysis of secondary endpoints:
 
The secondary efficacy endpoints will be analyzed using a similar approach to the primary efficacy endpoint, with missing values imputed by control-based multiple imputation method under the missing not at random framework.
 
For each of the continuous secondary endpoints, each of the complete datasets will be analyzed by the ANCOVA model.
 
The model will include treatment groups (sotagliflozin 400 mg, sotagliflozin 200 mg, placebo), randomization strata of HbA1c (<math>\leq 8.5\%</math>, <math>> 8.5\%</math>) at Screening, sex (male, female) and country as fixed effects, and Baseline secondary endpoint value as a covariate.
 
Results from each complete dataset will be combined to provide the adjusted LS mean change from Baseline to Week 26 (respectively Week 12 for SBP) for each treatment group, as well as the between-group difference (comparing each sotagliflozin group versus placebo group) and the 95% CI for the difference.
 
The categorical secondary efficacy variables of HbA1c <math>< 7.0\%</math> at Week 26 will be analyzed using a Cochran-Mantel-Haenszel method stratified by randomization strata of HbA1c (<math>\leq 8.5\%</math>, <math>> 8.5\%</math>) at Screening and sex (male, female).
 
Analysis of the key secondary safety endpoint of percent change from Baseline to Week 26 in BMD will be performed on the safety population, using an ANCOVA model.
 
To compare sotagliflozin 400 mg and 200 mg versus placebo, the model will include treatment groups (sotagliflozin 400 mg, sotagliflozin 200 mg, placebo), randomization strata of HbA1c

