--	---

	
(<math>\leq 8.5\%</math>, <math>> 8.5\%</math>), sex (male, female) and country as fixed effects, and Baseline BMD value as a covariate, providing the adjusted LS mean percent change from Baseline to Week 26 for each treatment group, as well as the between-group difference (comparing each sotagliflozin group vs placebo group) and the 95% CI for the difference.
 
The last-observation-carried-forward (LOCF) approach will be applied for the missing data imputation of the key safety endpoint of percent change in BMD from Baseline to Week 26. As the Week 26 Visit is the first post-Baseline scheduled visit for BMD measurement, if a patient withdraws early from the study before Week 26, the BMD measurement collected at the withdrawal visit will be used carrying forward to Week 26 in analysis.
 
Multiplicity considerations
 
To control the family-wise Type I error, a fixed sequence testing approach will be used to test primary and secondary endpoints. Only if the difference in mean change from Baseline to Week 26 in HbA1c of sotagliflozin 400 mg versus placebo is statistically significant at <math>\alpha=0.05</math> (2-sided), a hierarchical testing procedure will be performed to test the secondary endpoints in the following prioritized order:
 
Superiority of sotagliflozin 400 mg versus placebo with respect to:
 

• Change from Baseline to Week 26 in BW.

• Change from Baseline to Week 26 in FPG.

• Change from Baseline to Week 12 in SBP for all patients.

 
Superiority of sotagliflozin 200 mg versus placebo with respect to:
 

• Change from Baseline to Week 26 in HbA1c.

• Change from Baseline to Week 26 in BW.

• Change from Baseline to Week 26 in FPG.

• Change from Baseline to Week 12 in SBP for all patients.

 
Superiority tests will be tested at 2-sided 5% significant level. If any of the endpoints is found to be not statistically significant, the testing procedure will be stopped and the following endpoints will not be tested. Multiplicity adjustment will not be performed on other secondary endpoints not mentioned above.
 
Analysis of other efficacy endpoints:
 
The analysis of other efficacy endpoints will be descriptive with no formal testing. Summary statistics at scheduled visits using OC will be provided by each treatment group. Graphical presentations will also be used to illustrate trends over time.
 
Analysis of other safety endpoints:
 
The percent change from Baseline to Week 52 (or Week 104) in BMD will be analyzed using a mixed-effect model with repeated measures (MMRM). The MMRM model will include treatment groups (sotagliflozin 400 mg, sotagliflozin 200 mg, placebo), randomization strata of HbA1c (<math>\leq 8.5\%</math>, <math>> 8.5\%</math>), sex (male, female), visit, treatment-by-visit interaction and country as fixed effects, and Baseline BMD value-by-visit interaction as covariate, providing the

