- d Vital sign measurements (sitting BP and HR): 3 separate seated BP and HR measurements should be taken with at least 1 minute between readings, following a 5-minute rest period and prior to phlebotomy (see Appendix C).
- e The abbreviated physical exam should focus on cardiac and respiratory systems, as well as any areas important for assessment of AEs if necessary.

- f* Patients will be instructed to measure their fasting glucose levels via SMBG and discuss results with site personnel at clinic visits or phone contacts. The frequency of the fasting SMBG measurements will be determined by the Investigator according to the clinical need and background diabetes treatment, but it is recommended to be done at least once a week. Patients will also be instructed to self-assess blood glucose levels whenever they experience any illnesses (eg, cold, flu), or symptoms of hyperglycemia or hypoglycemia. Note that the SMBG measurements obtained with glucose meters are displayed as plasma glucose concentration. The SMBGs  $\leq 70$  mg/dL will be reported on the hypoglycemia specific electronic case report form page.
- g* The 12-lead ECG recordings should be obtained prior to IMP administration. The ECG will be evaluated as "normal" or "abnormal".
- h* All laboratory assessments occur prior to dose of double-blind IMP and NIMP.
- i* The FPG is performed in fasting status, ie, without any food intake (except for water) for at least 8 hours.
- j* The FSH and serum estradiol is performed in all women at Screening to confirm menopausal status as needed.
- k* Markers of bone turnover include: markers of bone resorption (serum NTX, serum  $\beta$ -CTX-1) and bone formation (serum P1NP and osteocalcin).
- l* Markers of calcium metabolism include: serum and urinary calcium (adjusted for creatinine), serum 25-hydroxyvitamin D, serum 1,25-dihydroxyvitamin D, serum and urinary phosphorus (adjusted for serum phosphorus, and creatinine), serum and urinary magnesium (adjusted for serum magnesium and creatinine), serum iPTH.
- m* 24-hour urine samples for calcium, phosphorus, and magnesium will be collected at Weeks 0, 26, 52, and 104. Patients will be instructed to initiate the 24-hour urine collection on the day before the visits. In exceptional situations, the 24-hour urine collection can be done up to 2 days maximum prior to or after the visit, and the specimen should be sent to the study site as soon as possible.

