### **9.2.1.6 Vital signs and physical examination**

Vital signs, including sitting BP and HR, will be assessed at all study visits for safety and efficacy endpoints. Full details and directions for the measurement of BP and HR are presented in [Appendix C](#). Physical examinations will be performed at every study visit.

A complete physical examination will be performed at Screening (Visit 1), Week 26 (Visit 8), and Week 104 (Visit 13). An abbreviated physical examination will be performed at all the other visits, including the Follow-up Visit/Week 106 (Visit 14). The abbreviated physical examination should focus on cardiac and respiratory systems, as well as any areas important for assessment of AEs, if necessary. The complete physical examination will also include recording of BW and vital signs. Body weight measurements are discussed in [Section 9.1.4.4](#). Height will be measured only at Screening Visit, Week 52, Week 104, and Premature EOT Visit.

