## 11.4 STATISTICAL METHODS

Continuous data will be summarized by treatment group using the number of observations available (N), mean, SD, minimum, median, and maximum.

Categorical data will be summarized by treatment group using count and percentage.

In general, descriptive statistics of quantitative efficacy and safety parameters (result and change from Baseline) by scheduled visits will be provided on observed cases (OC), ie, inclusion of only patients having nonmissing assessments at a specific visit.

The Baseline value is defined generally as the last available value before the first dose of double-blind IMP or the last available value prior to randomization for patients who were randomized but never exposed to IMP.

For serum creatinine and eGFR, the Baseline value is defined as average of all values before the first dose of double-blind IMP for those randomized and exposed or before randomization for patients who were randomized but never exposed to IMP.

Analysis of demographics and Baseline characteristics and prior and concomitant medications will be provided in detail in the Statistical Analysis Plan (SAP).

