For patients in the sotagliflozin groups with missing data at Week 26 (or Week 12 for SBP), their missing values will be imputed using observed baseline and the observed primary endpoint data from placebo completers; no intermittent values from either placebo or the active treatment groups will be used.

For placebo patients, missing data will be imputed based on the placebo group data. Intermittent observed values will be used while imputing missing values at Week 26 (or Week 12 for SBP). In cases that a non-monotone missing data pattern occurs at the intermediate visits, these data points will be first imputed in the placebo group using the Markov Chain Monte Carlo (MCMC) option in PROC MI to achieve a monotone missing pattern for all placebo patients. The Week 26 (or Week 12 for SBP) endpoint values will be subsequently imputed from the multiple copies of the original dataset where each copy will have a monotone missing pattern.

The imputation models for the washout MI method will include the randomization strata and the corresponding baseline value. Missing data will be imputed using the regression method. In cases of non-convergence during the imputations, especially for the MCMC application in the placebo non-monotone datasets, graphical measures (eg, trace and autocorrelation plots) will be used to identify the offending variable and once detected, that variable(s) will be dropped from the model and the imputations will be re-run. These re-run models will use the same seed number and number of imputations as used in the original models.

Using either imputation method, missing endpoint data will be imputed 2000 times to generate multiple data sets with complete data. Other details of the imputation procedures such as the seed number and sort ordering are specified in the SAS programs. The HbA1c change from Baseline to Week 26 will be derived from observed and imputed HbA1c values at Week 26.

Each of the completed datasets after the imputation will be analyzed using the Analysis of Covariance (ANCOVA) model with treatment groups (sotagliflozin 400 mg, sotagliflozin 200 mg, placebo), randomization stratum of HbA1c ($\leq 8.5\%$, $> 8.5\%$), randomization stratum of sex (male, female), and country as fixed factors, and baseline value of the efficacy endpoint as a covariate.

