2.4.4.2 Analyses of secondary efficacy endpoints

For continuous secondary efficacy endpoints (see Section 2.1.3) with missing data at Baseline, missing data will be imputed using MI under the assumption of missing at random (MAR). Missing data at Baseline will be imputed using regression method that includes randomization stratum of HbA1c ($\leq 8.5\%$, $> 8.5\%$), randomization stratum of sex (male, female) and baseline value in the imputation model.

Each continuous secondary efficacy endpoint (Section 2.1.3) will be analyzed using a similar ANCOVA model including the measurements at Baseline and endpoint (observed or imputed). The missing data at endpoint will be imputed by the retrieved dropouts if there are at least 5 patients in each study treatment group who discontinued but have the endpoint. Otherwise, the washout imputation method will be used. After the imputation, each of the complete datasets will be analyzed by an ANCOVA model with treatment groups (sotagliflozin 400 mg, sotagliflozin 200 mg, placebo), randomization stratum of HbA1c ($\leq 8.5\%$, $> 8.5\%$), randomization stratum of sex (male, female), and country as fixed effects, and baseline secondary endpoint value as a covariate.

Results from each complete dataset will be combined using Rubin's rule to provide the adjusted mean change from Baseline to week 26 (or week 12 for SBP) for each treatment group, as well as the between treatment group difference (comparing each sotagliflozin group to placebo group) and the 95% CI for the between-group difference.

For all continuous secondary endpoints, summary statistics at scheduled visits will be provided for each treatment group. The summary will include the number of observations, mean, SD, SE,

minimum, median, and maximum. Graphical presentations will also be used to examine trends over time using mean (\pm SE) and mean change from Baseline (\pm SE) at each of the scheduled visits. In addition, SBP will be summarized descriptively at each visit for those with baseline SBP \geq 140 mmHg.

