For the safety analyses, the baseline for a given parameter is defined as the last available measurement (or the average of all measurements for creatinine and eGFR), including unscheduled assessments, assessed prior to the first administration of double-blind IMP. For the efficacy analyses, the baseline for a given parameter is defined as the last available measurement (or the average of all measurements for eGFR), including unscheduled assessments, assessed prior to the first administration of double-blind IMP or the last available value (or the average of all measurements for eGFR) before randomization if not treated with double-blind IMP.

Summary statistics by visit for continuous efficacy endpoints

Summary statistics (number, mean, SD, SE, minimum, median, maximum) of continuous efficacy endpoints (observed data and change from Baseline) will be provided at scheduled visits as per protocol. Summaries showing data by visit will be presented according to the visit number (or re-allocated visit number, see [Section 2.5.4](#)) and labeled with the targeted approximate day/week.

Last on-treatment value for laboratory variables and vital signs

The last on-treatment value is the final measurement assessed during the treatment epoch, regardless of the introduction of rescue therapy, including measurements at unscheduled visits. See [Section 2.1.4](#) and [Section 2.5.4](#) for details.

Display of safety data by visit (laboratory variables and vital signs)

Descriptive statistics (number, mean, SD, minimum, median, maximum) of quantitative laboratory variables and vital signs (observed data and change from Baseline) during the TEAE period will be provided at scheduled visits. In addition, these summaries will also include a row for the 'last value on-treatment' to describe the last available on-treatment value (see above). Summaries showing data by visit will be presented according to the visit number (or re-allocated visit number, see [Section 2.5.4](#)) and labeled with the targeted approximate day/week.

As specified in the study protocol, laboratory data from scheduled visits are reported by central laboratories. The local results will not be used in the efficacy analyses or in the definition of

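### Free improvement: the valid Week 12 SBP model leaves out Screening and Run-in SBP, which gives up some precision on the 400 mg test that gates four 200 mg tests

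*Protocol*

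**What the plan says.** **The model.** The protocol summary and Protocol 11.4.2.2 fit each continuous secondary endpoint with treatment, HbA1c stratum, "sex (male, female) and country as fixed effects, and Baseline secondary endpoint value as a covariate". SAP 2.4.4.2 agrees ("and baseline secondary endpoint value as a covariate"), as does the general model in SAP 2.4.4.1 ("and baseline value of the efficacy endpoint as a covariate").

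**The baseline.** Protocol 11.4: "The Baseline value is defined generally as the last available value before the first dose of double-blind IMP". For efficacy, SAP 2.5.4 says "the baseline for a given parameter is defined as the last available measurement (or the average of all measurements for eGFR"). For SBP this is normally Visit 3. Averaging over all pre-dose values applies only to creatinine and eGFR.

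**What is collected.** Protocol 9.2.1.6: "Vital signs, including sitting BP and HR, will be assessed at all study visits for safety and efficacy endpoints". Footnote d of the flow chart (Protocol 1.2) says "3 separate seated BP and HR measurements should be taken with at least 1 minute between readings", and Appendix C makes the mean of the three the value for that visit. Before randomization SBP is therefore scheduled at Visit 1 (Screening), Visit 2 (Run-in) and Visit 3. The SAP already summarizes mean Screening SBP (2.1.1).

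**The sequence.** Protocol 11.4.2.4 and SAP 2.4.4.4 place 400 mg SBP fourth, after 400 mg HbA1c, body weight and FPG. The 200 mg tests of HbA1c, body weight, FPG and SBP follow it. After any failure, "the testing procedure will be stopped and the following endpoints will not be tested". The HbA1c <7.0% comparison is outside the sequence at both doses.

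**The concern.** SBP varies from visit to visit, so one visit measures a patient's usual level with error. Two earlier visits carry further information about that level, are fixed before randomization and cost nothing more to collect. Leaving them out keeps residual variance in the SBP test that the model could remove.

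This matters more for SBP than for most secondary endpoints because of its place in the sequence. A miss on 400 mg SBP closes four tests that correspond to stated superiority objectives for 200 mg. The documents state power for the primary HbA1c test but none for SBP.

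**Working it through.** **The plan's own figure.** HbA1c, 120 per arm, SD 1.2, difference 0.6, two-sided 0.05 (Protocol 11.1):

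Power = Φ(0.6 / (1.2 × √(2/120)) − 1.96) = Φ(3.873 − 1.96) = 97.2%. The stated 97% reproduces.

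**SBP inputs.** From the documents: 120 per arm, two-sided 0.05. Assumed, because the documents are silent: SD 14 mmHg at a visit, a true difference of 4 mmHg, and the correlations below. The only SBP effect in the documents is the 5.7 mmHg reduction on 400 mg in the 12-week Phase 2 study (Protocol 4.2), so that value is shown too. Strata and country are left out of the approximation.

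**Formulas.** Let w1, w2, w3 be the correlations of Visits 1, 2 and 3 with Week 12, and ρ12, ρ13, ρ23 those among the pre-dose visits. The new covariate is the mean of Visits 1 and 2.

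- Residual fraction, Visit 3 only: 1 − w3².
- v = (1 + ρ12)/2; b = ((w1 + w2)/2)/√v; c = ((ρ13 + ρ23)/2)/√v.
- Residual fraction with the added covariate: 1 − (w3² + b² − 2·w3·b·c)/(1 − c²).
- Power = Φ(Δ / (14 × √residual × √(2/120)) − 1.96).

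If all correlations equal r, the second residual reduces to 1 − 3r²/(1 + 2r). At r = 0.5: 0.750 becomes 1 − 0.75/2 = 0.625, a cut of 16.7%.

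First unequal row of the table: v = 0.825, b = 0.535/0.908 = 0.589, c = 0.625/0.908 = 0.688. R² = (0.360 + 0.347 − 0.486)/(1 − 0.4735) = 0.419, so the residual goes from 0.640 to 0.581, a cut of 9.2%.

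| w1 / w2 / w3 | ρ12 / ρ13 / ρ23 | Residual | Cut | Power at 4 mmHg | Power at 5.7 mmHg |
|---|---|---|---|---|---|
| all 0.4 | all 0.4 | 0.840 → 0.733 | 12.7% | 67.5 → 73.4% | 93.1 → 95.8% |
| all 0.5 | all 0.5 | 0.750 → 0.625 | 16.7% | 72.4 → 79.9% | 95.4 → 97.9% |
| all 0.6 | all 0.6 | 0.640 → 0.509 | 20.5% | 79.0 → 87.3% | 97.6 → 99.3% |
| all 0.7 | all 0.7 | 0.510 → 0.387 | 24.0% | 87.3 → 94.5% | 99.3 → 99.9% |
| 0.52 / 0.55 / 0.60 | 0.65 / 0.60 / 0.65 | 0.640 → 0.581 | 9.2% | 79.0 → 82.7% | 97.6 → 98.5% |
| 0.44 / 0.47 / 0.50 | all 0.6 | 0.750 → 0.695 | 7.3% | 72.4 → 75.6% | 95.4 → 96.6% |
| 0.44 / 0.47 / 0.50 | all 0.7 | 0.750 → 0.719 | 4.1% | 72.4 → 74.2% | 95.4 → 96.1% |
| 0.48 / 0.54 / 0.60 | 0.75 / 0.70 / 0.75 | 0.640 → 0.624 | 2.5% | 79.0 → 80.0% | 97.6 → 97.9% |

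The last four rows let the earlier visits predict Week 12 less well than Visit 3 does.

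**Type I error.** In 4,000 simulated trials per setting (r = 0.6, SD 14, covariate either Visit 3 or the mean of Visits 1 to 3), the null rejection rate was 4.7% and 5.2%. The Monte Carlo standard error is √(0.05 × 0.95/4000) = 0.34 points, so both agree with 5%. Power at 4 mmHg was 77% and 87%.

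**Imputation.** SAP 2.4.4.1 fits the retrieved-dropout model within each arm and allows it with 5 such patients. Intercept, two strata and baseline make 4 parameters, leaving 5 − 4 = 1 residual degree of freedom. A fifth term would leave none.

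**The case against.** The strongest reply is that nothing is broken. ANCOVA on the last pre-dose value is conventional and unbiased. The Visit 3 value is already a mean of three rested readings, so only between-visit variation is left to remove. All of that stands.

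The reply also goes to size. Screening SBP may predict Week 12 less well than Visit 3. It precedes the run-in, which Protocol 4.5 intends to reduce response to placebo and to trial participation. Protocol 6.1.2 and 8.8.1 hold antihypertensive doses constant only after randomization. Appendix C uses Visit 1 to choose the reference arm by measuring both. The equal-correlation rows are therefore an upper case. At 5.7 mmHg the test is already well powered at SD 14, although Protocol 4.2 does not say that this figure is placebo-subtracted.

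The imputation argument also stands. SAP 2.4.4.1 deliberately keeps the retrieved-dropout model simple because it expects few such patients.

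Three stronger readings are tempting, and the documents do not support them:

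- That every 200 mg test is gated. The 200 mg HbA1c <7.0% comparison is not.
- That averaging creatinine and eGFR shows an inconsistency. It defines baseline for parameters that have no formal test, so it shows only that the plan can handle several pre-dose values.
- That every randomized patient has all three SBP values. The documents give a schedule, not completeness.

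What survives is that a covariate fixed before randomization can add precision at almost no cost.

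**Conclusion.** The point holds as a free improvement, not as an error. The planned SBP test is valid and keeps its 5% level. It leaves out scheduled pre-randomization SBP that would make the estimate more precise, on the step that gates four alpha-controlled 200 mg tests.

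The residual variance fell in every scenario examined, but the size cannot be fixed from the documents. With SD 14 mmHg, 120 per arm and a 4 mmHg difference, the cut is about 2 to 9% if earlier visits predict Week 12 less well (about 1 to 4 power points). It is 13 to 24% under equal correlation of 0.4 to 0.7 (about 6 to 8 points). At 5.7 mmHg the gain is about 3 points or less.

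A reader might infer that the SBP gate is underpowered. The documents do not show that, because they give no SBP SD or target difference. The consequence of a miss also comes from the test order, and the covariate only shifts its probability.

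**What to change.** Before unblinding for the first-step analysis, amend the SBP model in SAP 2.4.4.2 and note the departure from Protocol 11.4.2.2:

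- Keep the endpoint as change from the Visit 3 baseline to Week 12, and keep that baseline in the model.
- Add one continuous covariate: the mean of the available Screening and Run-in SBP visit values. If only one of the two visits is available, use it alone.
- Leave the retrieved-dropout imputation model unchanged.
- If the washout method is used, add the covariate there. It is estimated in the placebo group (120 planned), which can support one more term.

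The cost is a short SAP amendment, one derived variable and one model degree of freedom. No new data are needed, and the endpoint, test order and significance level do not change. If treatment codes have already been opened for the Week 26 analysis, the extended model should be reported only as supportive.
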